6.0 Analytic Plan

6.1 Sample Size and Power

This pilot study has an accrual goal of 42 endometrial cancer survivors. This study focuses on the feasibility of implementing the PREVENT tool to promote discussion of cardiovascular health risks between providers and cancer survivors. Feasibility will be defined from the proportion of patients who complete the web-based assessment. A sample size of 42 total participants will have 83% power to detect a hypothesized participation rate of 80% or more with an unacceptable participation rate considered 60% or less. This assumes a conservative 10% dropout of participants prior to the time of visit, with a one-sided alpha=0.05, and one-sample exact binomial test. Assuming 37 survivors complete the assessment, we will be able to estimate participation within +/- 17% using exact 95% binomial confidence intervals. A sample size of 37 survivors would allow for reasonable estimates of SDs that could be used for future studies.

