2.0 Objectives

2.1 Primary Objective

The primary objective of this *pilot* study is to assess the feasibility of enrolling and completing the heart health assessment among endometrial cancer patients scheduled for routine follow-up care.

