5.0 Outcome Measures

5.1 Primary Outcome

Proportion of patients who consent to the study and complete the web-based heart health assessment.

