6.2 Analysis of Primary Outcome

For our primary objective, analyses will be largely descriptive (using means, medians, frequencies etc.).

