6.4 Accrual Rate

Accrual is expected to be 10 patients per month, based on an estimated 20 endometrial cancer survivors seen by the gynecologic oncology department for surveillance in the average month.

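### Section 6.1's inputs give 80.9% power at 37 evaluable patients, not 83%, and no section fixes the denominator of the primary proportion, which decides the test result for 28 to 30 completers when 37 of 42 attend

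*Combined protocol and SAP*

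**What the plan says.** The outcome is described in three ways, none of which names a denominator:

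- Section 2.1 sets out to "assess the feasibility of enrolling and completing the heart health assessment among endometrial cancer patients scheduled for routine follow-up care".
- Section 5.1 defines the primary outcome as "Proportion of patients who consent to the study and complete the web-based heart health assessment".
- Section 6.1 says "Feasibility will be defined from the proportion of patients who complete the web-based assessment", and then calls this a participation rate.

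On sample size, Section 6.1 says "A sample size of 42 total participants will have 83% power to detect a hypothesized participation rate of 80% or more", with 60% or less regarded as unacceptable. It adds "This assumes a conservative 10% dropout of participants prior to the time of visit, with a one-sided alpha=0.05, and one-sample exact binomial test". On precision it says "Assuming 37 survivors complete the assessment, we will be able to estimate participation within +/- 17% using exact 95% binomial confidence intervals".

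The whole analysis text for the primary outcome, in Section 6.2, is "For our primary objective, analyses will be largely descriptive (using means, medians, frequencies etc.)". It names no denominator, test or threshold. Section 6.4 gives the recruitment flow: "Accrual is expected to be 10 patients per month, based on an estimated 20 endometrial cancer survivors seen by the gynecologic oncology department".

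**The concern.** There are two problems.

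**Power.** Section 6.1 gives every input needed to check its power figure, and those inputs do not give 83%.

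**Denominator.** The wording points in different directions. In Section 5.1 consent is part of what is counted, which suggests a denominator of patients approached. Section 2.1 includes enrolling, which points the same way. Section 6.1 removes dropouts before testing, which suggests patients who reach the visit. Its reference to 42 total participants could be read as all enrolled. Section 6.1 also describes the 37 as patients who complete the assessment, which makes them a numerator, while its precision figure uses 37 as a denominator.

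At stake is the feasibility conclusion. The same number of completers can pass or fail the 60% benchmark depending on the denominator, and as written that choice could be made after the data are seen.

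**Working it through.** **Inputs (all from Section 6.1).** Enrolled N = 42; dropout before the visit 10%, so 42 × 0.9 = 37.8, and the plan uses 37; p0 = 0.60; p1 = 0.80; one-sided alpha 0.05; one-sample exact binomial test.

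**Step 1: the plan's power figure.** The cut-off r is the smallest count with P(X ≥ r | n, 0.60) ≤ 0.05. Power is P(X ≥ r | n, 0.80).

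| n | cut-off r | exact size | power |
|---|---|---|---|
| 34 | 26 | 0.034 | 77.3% |
| 35 | 27 | 0.026 | 74.5% |
| 36 | 27 | 0.045 | 83.2% |
| 37 | 28 | 0.035 | 80.9% |
| 38 | 29 | 0.027 | 78.4% |
| 39 | 29 | 0.045 | 85.9% |
| 40 | 30 | 0.035 | 83.9% |
| 41 | 31 | 0.027 | 81.8% |
| 42 | 31 | 0.045 | 88.2% |

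Only n = 36 rounds to 83%, and 36/0.9 = 40, not 42. Other routes also miss:

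- averaging exact power over attendance ~ Bin(42, 0.9): 81.5%
- normal approximation at 37: 84.8%, or 79.4% with continuity correction
- arcsine approximation at 37: 85.2%

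How 83% was reached is unknown.

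**Step 2: the precision figure.** The largest Clopper-Pearson 95% half-width at n = 37 is 16.8 points, and the longest single arm is 17.4 points. The ± 17% therefore reproduces with 37 as the denominator. It does not identify 37 uniquely, because the largest half-widths for n = 35 to 38 (17.3, 17.1, 16.8 and 16.6 points) all round to 17. If 37 were the completers, as the sentence says, the estimate out of 42 would be 37/42 = 88.1%, with exact 95% interval 74.4% to 96.0%.

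**Step 3: attenders against all enrolled, with 37 of 42 attending.** One-sided exact p-values against 60%:

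| completers | out of 37 | out of 42 |
|---|---|---|
| 28 | 0.035 | 0.236 |
| 29 | 0.015 | 0.149 |
| 30 | 0.005 | 0.086 |

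At 27 completers even the 37 denominator fails (27/37, p = 0.072). At 31 even the 42 denominator passes (31/42, p = 0.045). The two denominators therefore disagree exactly at 28 to 30. If 80% of the 37 attenders complete, P(28 ≤ X ≤ 30) = 0.123 + 0.153 + 0.163 = 0.439.

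This depends on attendance. With 38 attending, the range of disagreement is 29 to 30 (probability 28.4%); with 39 it is 29 to 30 (23.5%); with 40 it is 30 only (10.7%); with 41 or 42 there is none. With 36 it widens to 27 to 30 (58.6%). Averaged over Bin(42, 0.9), the probability of disagreement is 34.1%.

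**Step 4: power if all 42 are the denominator.** The cut-off is 31.

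- If 80% of all enrolled complete, power is 88.2%.
- If the 10% dropouts count as non-completers and 80% of attenders complete, the overall rate is 0.9 × 0.8 = 0.72, and P(X ≥ 31 | 42, 0.72) = 47.5%.

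**Step 5: patients approached as the denominator.** The documents do not give the number approached, so the following is an assumed range per 10 enrolled. The ceiling is 10 divided by the number approached; the last column multiplies it by 0.72.

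| approached (assumed) | ceiling | at 72% completion |
|---|---|---|
| 20 | 50% | 36% |
| 15 | 67% | 48% |
| 12.5 | 80% | 57.6% |

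If all 20 survivors seen per month in Section 6.4 were eligible and approached, the proportion could not exceed 50%, which is below the rate the plan calls unacceptable.

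**The case against.** The strongest reply has four parts.

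**The power error is harmless.** It is 2.1 points, leaves power above 80% at 37, and changes nothing in the design. This stands; alone it would be an editorial correction.

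**Section 6.1 already implies the denominator.** It deducts dropouts before testing, and its precision figure works with 37 as denominator, so attenders can be inferred. That is true of the calculation. But Sections 2.1 and 5.1 point elsewhere, and Section 6.2, where the rule belongs, is silent.

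**There is no decision rule.** The primary analysis is called largely descriptive, and the test appears only in the sample-size justification. It is right that the reject/not-reject contrast assumes the Section 6.1 test will be applied. But that section also sets the two rates and ties feasibility to this proportion, and a purely descriptive proportion still needs a denominator.

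**Some figures are conditional.** The 43.9% holds only if exactly 37 attend; the average of 34.1% is lower but still material. The 47.5% takes 80% as the rate among attenders, and 88.2% is equally open if 80% refers to all enrolled. The approached scenario cannot be the denominator behind the Section 6.1 calculation, and not every survivor seen will be eligible. It shows how far the literal wording of Section 5.1 could move the result; it is not a forecast.

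**Conclusion.** The concern holds on both counts.

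The stated 83% is wrong for the stated inputs: power is 80.9% at 37 evaluable and 78.4% at 38. The design is not materially underpowered at 37, and the sample size need not change.

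The undefined denominator matters more. Attenders and all enrolled lead to opposite test results in about a third of trials (34.1%), and in 43.9% if exactly 37 attend. These figures assume that the Section 6.1 exact test against 60% is applied, that 80% of attenders complete, and, for the average, that each enrolled patient attends independently with probability 0.9. The point should be corrected before analysis.

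**What to change.** **Section 6.1.** Restate the power as about 81% at 37 evaluable patients (78% at 38), and describe the 37 as evaluable survivors, not as survivors who complete the assessment.

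**Section 6.2.** Name the denominator before analysis. State that the primary proportion will be reported with its exact 95% confidence interval and tested against 60% with the one-sided 0.05 exact binomial test already named in Section 6.1. The cut-off should follow the actual denominator: 27/36, 28/37, 29/38, 29/39, 30/40, 31/41 or 31/42.

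The existing calculation implies consented patients who reach the visit. If that is kept, also report completers out of all enrolled and out of all eligible patients approached, with exact 95% intervals and no test, because Section 2.1 covers enrolment as well as completion. If all enrolled is chosen instead, state both power figures, 88.2% and 47.5%, with the assumption behind each.

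**Screening record.** Section 4.3 provides for recording screening failures and schedules a form for it, and Section 7.0 says where the form is stored. Neither says that eligible patients who decline are counted. Add the numbers approached, eligible and declined.

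**Cost.** A few sentences and one added count; no extra patients. The stated power becomes slightly less favourable, and an attender denominator does not count pre-visit dropouts as failures. Choosing all enrolled would count them, but power could then be as low as 47.5%.

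### The 83% power in section 6.1 does not reproduce at the plan's own 37 evaluable survivors, where the named exact test gives 80.9%; minor, a one-sentence correction

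*Combined protocol and SAP*

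**What the plan says.** All the inputs are in section 6.1 (Sample Size and Power).

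- Enrolment: "This pilot study has an accrual goal of 42 endometrial cancer survivors".
- Stated power: "A sample size of 42 total participants will have 83% power to detect a hypothesized participation rate of 80% or more".
- Rate under the null: "unacceptable participation rate considered 60% or less".
- Loss, alpha and test: "This assumes a conservative 10% dropout of participants prior to the time of visit, with a one-sided alpha=0.05, and one-sample exact binomial test".
- Working number after loss: "Assuming 37 survivors complete the assessment". The precision statement (plus or minus 17 percentage points, exact 95% interval) and the remark on estimating SDs both use 37.

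The section gives no rejecting count and no attained alpha. Section 6.2 describes the primary analysis as mainly descriptive.

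**The concern.** A power statement for an exact binomial test can be recomputed from the number evaluable, the two rates and alpha. Section 6.1 supplies these, yet 83% does not come out at 37 or at 38, the two whole numbers on either side of 42 x 0.9. It is also the only power figure in the plan, and it errs in the favourable direction. At stake is whether a reader can trust, and reproduce, the stated chance that the study separates an 80% participation rate from a 60% one.

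**Working it through.** **Inputs (all from section 6.1).** 42 enrolled; 10% loss before the visit; null rate 0.60; alternative rate 0.80; one-sided alpha 0.05; exact one-sample binomial test; working number 37.

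**Number evaluable.** 42 x 0.9 = 37.8, so 37 if rounded down and 38 if rounded up. In the other direction, 37 / 0.9 = 41.1, which rounds up to 42. So 42 and 37 agree with each other under 10% loss.

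**Method.** For n evaluable, find the smallest k with P(X >= k | n, 0.60) <= 0.05. Attained alpha is that tail probability. Power is P(X >= k | n, 0.80).

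**At n = 37.** P(X >= 27 | 37, 0.60) = 0.0722, which is too large. P(X >= 28 | 37, 0.60) = 0.0348, so k = 28 (28/37 = 75.7%). Power = P(X >= 28 | 37, 0.80) = 0.8091.

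**Neighbouring numbers, same rule.**

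| Evaluable n | Reject at k or more | Attained alpha | Power at 80% |
|---|---|---|---|
| 36 | 27 | 0.0449 | 83.2% |
| 37 | 28 | 0.0348 | 80.9% |
| 38 | 29 | 0.0268 | 78.4% |
| 39 | 29 | 0.0450 | 85.9% |
| 40 | 30 | 0.0352 | 83.9% |
| 41 | 31 | 0.0274 | 81.8% |
| 42 | 31 | 0.0449 | 88.2% |

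**Where 83% is found.** Over n = 33 to 46, only n = 36 gives a power that rounds to 83%. But (42 - 36) / 42 = 14.3%, and 36 / 0.9 = 40, so 36 does not follow from 42 enrolled with 10% loss.

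**Other ways of reaching 83%.** At n = 37:
- exact test at one-sided alpha 0.025: 68.6%
- normal approximation: 84.8%, or 79.4% with continuity correction
- normal approximation with unpooled variance: 91.9%
- arcsine approximation: 85.2%
- mid-p: 80.9%

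Treating the number evaluable as random, Binomial(42, 0.9), and averaging the exact power gives 81.5%. None of these is 83%, and the plan names the exact test.

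**Check that 37 is meant as the denominator.** The exact 95% interval at n = 37 has a largest half-width of 16.8 points, which agrees with the stated 17. This supports the reading but does not prove it, because the largest half-widths at 36 (17.1) and 38 (16.6) also round to 17.

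**Size.** 83 - 80.9 = 2.1 points at n = 37. The chance of missing a true 80% rate is 100 - 80.9 = 19.1%, against the 17% implied by the plan.

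**The case against.** The strongest reply is that the discrepancy has little consequence. At 37, the only post-loss number the plan names, the gap is 2.1 points and power is still above 80%. The plan's second justification for its size, the interval precision at 37, does reproduce. The primary analysis is mainly descriptive, so no listed analysis changes. Averaged over random attendance, power is 81.5%, only 1.5 points below the stated figure. All of this stands, and it is why the point is minor.

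A reader might go further and infer that the study is underpowered, with power below 80%. The documents do not support that. It needs 38 evaluable patients, a number the plan never uses, and power at 39 to 42 is again above 80%. A reader might also infer that the sponsor ran the calculation at 36. That is only a numerical match; 36 appears nowhere in the plan.

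One further reservation is fair. Taken literally, section 6.1 has 37 survivors completing the assessment, which could make 37 a count of completers instead of a denominator. Reading it as the denominator is an interpretation, supported by the precision figure. The other reading does not rescue 83%: with all 42 as the denominator, power is 88.2% at a true rate of 80%, or 47.5% if losses count as non-completers (true rate 0.9 x 0.8 = 0.72).

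**Conclusion.** The sentence is wrong as written, and the error is minor. Under the test, alpha and rates in section 6.1, power at 37 evaluable survivors is 80.9%, not 83%. No whole number implied by 10% loss from 42 yields 83%: rounding 37.8 down gives 80.9% and rounding it up gives 78.4%. The conclusion assumes that 37 is the number evaluable and that the test is the standard exact one, rejecting at the smallest count whose null tail probability is at most 0.05. It is a correction to the reporting and does not call the sample size into question.

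**What to change.** Replace the power sentence in section 6.1 with wording such as: with 37 evaluable survivors, the exact test rejects 60% if 28 or more complete (attained one-sided alpha 0.035), with 81% power at a true rate of 80%. Enrolment stays at 42.

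Optionally, add that exact power is not monotone in the number evaluable and include the table above for 36 to 42, so that the rejecting count is already set if attendance differs from 37.

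The cost is one sentence, plus a short table if wanted. The stated power becomes about 2 points less favourable; no procedure or data collection changes.

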6.2 Analysis of Primary Outcome

For our primary objective, analyses will be largely descriptive (using means, medians, frequencies etc.).

6.3 Analysis of Secondary Outcomes

For secondary objective 2.2.1, patient satisfaction with the tool, one-sample t-tests will be used to test whether the average response to each question is greater than 3.5 (with three denoting a neutral response). Wilcoxon signed rank tests will be used to compare cancer survivors' knowledge regarding their cardiovascular health risk factors and perceived importance of cancer

A pilot study to examine feasibility of a patient directed tool to assess heart health among endometrial cancer survivors

Wake Forest Baptist Comprehensive Cancer Center (WFBCCC)
WFBCCC # 99123

and heart disease before and after using the CV risk visualization tool. Categorical comparisons will be evaluated with Fisher's Exact test.

For secondary objective 2.2.2, analyses will be largely descriptive (using means, medians, frequencies etc.).

6.4 Accrual Rate

Accrual is expected to be 10 patients per month, based on an estimated 20 endometrial cancer survivors seen by the gynecologic oncology department for surveillance in the average month.

6.5 Length of Study

Targeted accrual should be met in approximately 6 months. A maximum of 42 patients will be enrolled on this trial.

7.0 Data Management

Data Collection Form	Data Storage Location
Informed Consent Document	EPIC
Subject Eligibility Checklist	WISER/OnCore
Protocol Registration Form	WISER/OnCore
Race & Ethnicity Form	WISER/OnCore
Screen Failure Form	REDCap
Pre-visit Baseline Survivor Survey	REDCap
Data entered into PREVENT	Google Firebase
Post-Baseline Survivor Survey	REDCap
Tool Assessment (v1.0)	REDCap
Gift Card Tracking Form	REDCap
Medical Record Extraction	REDCap
Off Treatment Form	WISER/OnCore
Off Study Form	WISER/OnCore
Withdrawal of Consent	WISER/OnCore
Survival Form	WISER/OnCore

This project will utilize REDCap Clinical Data Interoperability Services. This is a special feature for importing data into REDCap from WakeOne. It provides an adjudication process whereby REDCap users can approve all incoming data from WakeOne before it is officially saved in their REDCap project. REDCap Clinical Data Interoperability Services can only be enabled by a REDCap administrator who serves as an honest broker to PHI. REDCap's Clinical Data Interoperability Services can only be accessed by users with valid WakeOne credentials. Using the Clinical Data Interoperability Service requires using the Medical Record Number (MRN) as a key to automatically gather demographics and laboratory data and reduces data entry errors.

8.0 Confidentiality and Privacy

Confidentiality will be protected by collecting only information needed to assess study outcomes, minimizing to the fullest extent possible the collection of any information that could directly identify subjects, and maintaining all study information in a secure manner. To help ensure subject privacy and confidentiality, only a unique study identifier will appear on the data collection form. Any collected patient identifying information corresponding to the unique study identifier will be maintained on a linkage file, stored separately from the data. The linkage file will be kept secure, with access limited to designated study personnel. Following data collection, subject identifying information will be destroyed two years after closure of the study, consistent with data validation and study design, producing an anonymous analytical data set. Data access will be limited to study staff. Data and records will be kept locked and secured, with any

A pilot study to examine feasibility of a patient directed tool to assess heart health among endometrial cancer survivors

Wake Forest Baptist Comprehensive Cancer Center (WFBCCC)
WFBCCC # 99123

computer data password protected. No reference to any individual participant will appear in reports, presentations, or publications that may arise from the study.

9.0 Data Safety and Monitoring

The principal investigator will be responsible for the overall monitoring of the data and safety of study participants. The principal investigator will be assisted by other members of the study staff.

Data will be stored on a secure information technology-maintained computing infrastructure behind the WFBH firewall, which has been certified to store protected health information. Data from the PREVENT tool will also be stored on a secure information technology-maintained platform (Google Firebase) that complies with HIPPA standards. We will take consistent measures to protect the confidentiality of these data. When the data are collected and ready for analysis, the dataset will be downloaded by [name] and used only for the purposes identified in these analyses. Only approved members of the research team will have access to these data.

Appendix A – Subject Eligibility Checklist

IRB Protocol No.	WFBCCC Protocol No
<hr/>	
Study Title: A pilot study to examine feasibility of a patient directed tool to assess heart health among endometrial cancer survivors	
Principal Investigator: [name], MPH	

Inclusion Criteria (as outlined in study protocol)	Criteria is met	Criteria is NOT met	Source Used to Confirm * (Please document dates and lab results)
Scheduled for a routine surveillance visit for endometrial cancer			
≥ 3 months post-potentially curative cancer treatment			
Age >/= 18 years			
Have a working email address			
Comfortable reading medical information in English, as per self report			
Exclusion Criteria (as outlined in study protocol)	Criteria NOT present	Criteria is present	Source Used to Confirm * (Please document dates and lab results)
Currently receiving treatment (e.g. radiation, chemotherapy, immunological treatments for endometrial cancer)			
Have a history of endometrial cancer recurrence			
Enrolled in hospice care or documentation of life expectancy < 6 months			

This subject is eligible / ineligible for participation in this study.

OnCore Assigned PID: _____

Signature of research professional confirming eligibility: _____

**A pilot study to examine feasibility of a patient directed tool to assess heart health among endometrial
cancer survivors**

Wake Forest Baptist Comprehensive Cancer Center (WFBCCC)
WFBCCC # 99123

Date: ____/____/____

Signature of Treating Physician**: _____

Date: ____/____/____

* Examples of source documents include clinic note, pathology report, laboratory results, etc. When listing the source, specifically state which document in the medical record was used to assess eligibility. Also include the date on the document. Example: "Pathology report, 01/01/14" or "Clinic note, 01/01/14"

**Principal Investigator signature can be obtained following registration if needed

A pilot study to examine feasibility of a patient directed tool to assess heart health among endometrial cancer survivors

Wake Forest Baptist Comprehensive Cancer Center (WFBCCC)
WFBCCC # 99123

